## 9.7.1.8.2 Laboratory Values

Laboratory results were to be summarized using Système International units, as appropriate. For all quantitative parameters listed in Section 9.5.1.4 Safety Assessments, the actual value and the change from baseline to each post-baseline visit and to the end of treatment (i.e., defined as the last on-treatment value) was summarized using descriptive statistics. Qualitative parameters listed

Final; 26 Feb 2018 Page 55 of 80

in Section 9.5.1.4 were summarized using frequencies (i.e., number and percentage of subjects), and changes from baseline to each post-baseline visit and to end of treatment were reported. Percentages were based on the number of subjects with both nonmissing baseline and relevant post-baseline results.

Laboratory test results were assigned a low/normal/high (LNH) classification according to whether the value was below (L), within (N), or above (H) the laboratory parameter's reference range.

#### 9.7.1.8.3 Vital Signs

Descriptive statistics for vital signs parameters (i.e., diastolic and systolic BP, heart rate, respiration rate, temperature, and weight) and changes from baseline were to be presented by visit.

## 9.7.1.9 Efficacy Analyses

The primary objective of the study was to evaluate the effect of aripiprazole once monthly on 30-, 90-, and 180-day psychiatric re-hospitalization rates following discharge due to symptoms associated with schizophrenia, compared with retrospective 30-, 90-, and 180-day psychiatric hospitalization rates in subjects previously treated with oral antipsychotic medication.

Because all primary and secondary outcome measures described in the specific aims were continuous and a reflection of a single design configuration involving longitudinal measures, in some cases including retrospective as well as prospective time points, the basic structure of the data analytic strategies was the same for all objectives.

The primary and secondary outcomes were to be analyzed using repeated measures analysis of covariance (ANCOVA) models. For example, in the three primary outcome models, testing for a main effect of time on 30-, 90-, or 180-day pre-hospitalization (i.e., oral antipsychotic) versus 30-, 90-, or 180-day post-hospitalization (i.e., aripiprazole once monthly) rates, respectively. Covariates would have included psychiatric symptoms severity at baseline, measured by CGI-S scores.

Some secondary outcome measures such as BMI, fasting lipid parameters, and glucose that were measured at time points post-hospitalization only (i.e., at baseline, 30-, 90-, and 180-days) were to be evaluated using mixed model repeated measures analysis of variance to determine whether there are changes over time. Other covariates could include race, gender, age, family history of diabetes, and BMI.

Only one primary specific objective was defined, with three time-point comparisons (i.e., 30, 90, and 180 days) with the primary comparison being hospitalization rate for the period of 30 days pre-hospitalization (i.e., at least one, based on the index hospitalization) to 30 days post-hospitalization both because of the importance of that objective and to minimize multiple comparisons concerns. Because of the multiple comparisons issue, p-values associated with the secondary and exploratory analyses performed were to be interpreted cautiously as hypothesis-generating rather than as hypothesis-confirming.

Final; 26 Feb 2018 Page 56 of 80

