## 9 INVESTIGATIONAL PLAN

#### 9.1 OVERALL STUDY DESIGN AND PLAN

This was an open-label, multi-center, longitudinal, within-subject comparison study of the effects of aripiprazole once monthly on 30-, 90-, and 180-day psychiatric re-hospitalization rates following hospital discharge in subjects with schizophrenia compared with prior psychiatric hospitalization rates while on oral antipsychotics.

Prospective subjects underwent screening for eligibility for entry into the study during or immediately after hospitalization for symptoms due to schizophrenia.

An overview of the planned study design is provided in Figure 1.

.

Final; 26 Feb 2018 Page 23 of 80

[figure not shown]

Figure 1 Study Schematic

AE = adverse event, AIMS = Abnormal Involuntary Movement Scale, BARS = Barnes Akathisia Rating Scale, BMI = body mass index, CGI-I = Clinical Global Impression—Improvement, CGI-S = Clinical Global Impression—Severity, C-SSRS = Columbia Suicide Severity Rating Scale, HbA1c = glycosylated hemoglobin, PSP = Personal and Social Performance Scale, REALM-SF = Rapid Estimate of Adult Literacy in Medicine—Short Form, SAS = Simpson Angus Scale, UBACC = University of California, San Diego Brief Assessment of Capacity to Consent

Final; 26 Feb 2018

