# 9.1.2 Screening Period

All recruitment methods conformed to the guidelines of the IRB at the clinical site. The subjects participating in this study had to be capable of understanding the nature of the study. The ICF contained a full description of the procedures and their associated risks. Subjects were given both verbal and written descriptions of the procedures, discomforts, risks, and potential benefits by study personnel. After briefing subjects on the reasons for the research, their rights as a subject, and the risks involved, they were given the opportunity to ask questions. Subjects were asked to paraphrase the ICF. When ready, subjects were asked to give written consent to participate in the study. After the ICF was signed by both the subject and the investigator, each subject was given a copy of the signed ICF. The investigator had full responsibility for all issues pertaining to assent and informed consent. Procedures to be followed when obtaining informed consent are detailed in Section 5.1.

During the Screening Period, subjects could be treated with any oral antipsychotic medication of the clinician's choice, with the exception of clozapine. However, oral olanzapine was permitted during the Screening Period only for subjects who were eligible for Phase A.

Eligibility for the study was determined during the screening period, which could occur at any time, beginning with the first day of hospitalization. Eligibility for the study was assessed via the following:

- Confirmation of a current diagnosis of schizophrenia according to Diagnostic and Statistical Manual, Fifth Edition (DSM-5) criteria
- Review of inclusion and exclusion criteria
- Complete medical history, including demographics, complete psychiatric history including all psychiatric and non-psychiatric hospitalizations and medical interventions occurring within the 6 months prior to the date of signing the ICF:
  - O Data regarding psychiatric and non-psychiatric hospitalizations, including treatment records relevant to determination of study eligibility and identified outcome variables related to ED, outpatient and inpatient treatment episodes as described in the inclusion and exclusion criteria (Section 9.3.1 and Section 9.3.2, respectively) occurring within the 6 months prior to the date of signing the ICF were obtained by searching MO

Final; 26 Feb 2018 Page 25 of 80

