# 9.3.1 Inclusion Criteria

Subjects must have met all of the following criteria to be included in this study:

- 1. Were able to provide written informed consent.
- 2. Were male and female subjects 18 to 65 years of age, inclusive, at time of informed consent

Final; 26 Feb 2018 Page 30 of 80

- 3. Had a current and confirmed diagnosis of schizophrenia as defined by DSM-5 criteria and a history of the illness for at least 6 months prior to screening from a reliable source (e.g., subject, family member, friend, caregiver, healthcare provider, or medical records)
- 4. Present at one of the selected inpatient units with acute psychotic symptoms for hospitalization at study entry
- 5. Had a clinically indicated need for a change in current antipsychotic therapy
- 6. Were on Medicaid with searchable claims data or were Medicaid-eligible
- 7. Had at least one inpatient psychiatric hospitalization or psychiatric ED visit within the 6 months prior to screening as confirmed through Medicaid or all available medical records and reliable data from caregivers
- 8. Had been previously prescribed oral antipsychotic treatment for at least a substantial portion of the 6 consecutive months prior to screening, with estimated duration of prescribed treatment within the 6 months prior to screening as determined by Principal Investigator discretion and confirmed through Medicaid or all available medical records and reliable data from caregivers
- 9. Had a history of response to antipsychotic treatment, with no history of clozapine treatment
- 10. Were able to understand the nature of the study and follow protocol requirements, including the prescribed dosage regimens, tablet ingestion, aripiprazole once monthly injection, and discontinuation of prohibited concomitant medications
- 11. Were able to read and understand the written word with a passing score of 4 to 6 (i.e., equivalent to seventh to eighth grade reading level for REALM-SF literacy assessment) in order to complete subject-reported outcomes measures
- 12. Were willing to accept a monthly injection
- 13. Were male and female subjects who were surgically sterile (i.e., have undergone orchiectomy or hysterectomy, respectively); female subjects who were postmenopausal for at least 12 consecutive months; or male and female subjects who agreed to use an approved form of birth control during study participation

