#### 9.7.1 Statistical and Analytical Plans

#### 9.7.1.1 Primary Endpoint(s)

The primary efficacy endpoint was:

 Comparison of rates of psychiatric re hospitalization for symptoms associated with schizophrenia after receiving aripiprazole once monthly for 30, 90, and 180 days following hospital discharge for acute psychiatric stabilization, compared with retrospective 30-, 90-, and 180-day hospitalization rates, respectively, in subjects previously treated with oral antipsychotic medication.

Final; 26 Feb 2018 Page 52 of 80

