## 9.7.2 Determination of Sample Size

The primary endpoints of this study were comparisons of the rate of hospitalization for specified pre-hospitalization (i.e., pre-aripiprazole once monthly) timeframes (i.e., 30-, 90-, and 180-days) to corresponding post-hospitalization timeframes. Based on published results of other studies, it was generally reasonable to assume 30% of subjects would be hospitalized pre-medication switch and 15% would be hospitalized post-switch to aripiprazole once monthly. In this study, 100% of the pre-aripiprazole once monthly subjects would have had at least one hospitalization (i.e., index inpatient hospitalization at least). The estimated sample size of 90 completed subjects would have provided approximately 80% power (alpha = 0.05 two-sided) to detect a clinically relevant difference between pre-switch and post-switch hospitalization rates. The recent Otsuka Mirror study had 121 completers with only a 28% pre-switch hospitalization rate, compared to the present design with a 100% pre-switch hospitalization rate, with highly significant reductions in total psychiatric hospitalization rates in the Mirror study. A medium effect size = 0.5 with a sample size of N = 90 provided approximately 80% power to detect significance at the 5% level (two-tailed test).

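### The primary 30-day comparison counts the index admission, on which every subject is selected, in the pre-treatment rate, so a significant fall is close to certain even with no drug effect

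*Combined protocol and SAP*

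**What the plan says.** Of the three time points, section 9.7.1.9 makes 30 days primary, "with the primary comparison being hospitalization rate for the period of 30 days pre-hospitalization (i.e., at least one, based on the index hospitalization"), compared with the 30 days post-hospitalization. The test is the main effect of time in a repeated measures ANCOVA, with CGI-S severity as a covariate.

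Section 9.7.2 says the same about the pre period: "In this study, 100% of the pre-aripiprazole once monthly subjects would have had at least one hospitalization (i.e., index inpatient hospitalization at least"). It treats this as a strength against a mirror study with a 28% pre-switch rate, "compared to the present design with a 100% pre-switch hospitalization rate". Yet it also assumes 30% hospitalized before the switch and 15% after, and claims about 80% power with 90 completers at two-sided 5%.

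Other sections fix who enters and what is counted:

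- Inclusion criterion 4 (9.3.1): "Present at one of the selected inpatient units with acute psychotic symptoms for hospitalization at study entry".
- Inclusion criterion 8 (9.3.1): "Had been previously prescribed oral antipsychotic treatment for at least a substantial portion of the 6 consecutive months prior to screening".
- Post-treatment event (9.7.1.1): re-hospitalization "after receiving aripiprazole once monthly for 30, 90, and 180 days following hospital discharge for acute psychiatric stabilization".
- Timing of screening (9.1): "Prospective subjects underwent screening for eligibility for entry into the study during or immediately after hospitalization for symptoms due to schizophrenia". Section 9.1.2 adds that screening is a period "which could occur at any time, beginning with the first day of hospitalization".
- Retrospective data (9.1.2): the 6 months before the consent form is signed.

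**The concern.** The two sides of the comparison are not built alike. A subject is in the study because the pre-period event happened, so the pre value is at least 1 for everyone. Nothing guarantees an event in the post period. The index admission may well be a genuine failure during prescribed oral treatment, but an event that every subject must have in order to enter cannot serve as a comparator rate.

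Nothing else in the plan corrects for this. The look-back runs from consent, during or just after the index stay, and so takes that stay in. There is one arm (9.2). CGI-S is scheduled once, at screening (Table 3), so adjusting for it cannot remove an admission that all subjects share. Section 9.2 relies on objective assessment to deal with bias, but accurate counting does not cure selection on the outcome.

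At stake is the primary hypothesis in section 7.4. A significant fall would be expected whether or not the drug works.

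**Working it through.** **1. The plan's own power figure.** Inputs from 9.7.2: 30% pre, 15% post, N = 90, two-sided 5%. The design is paired, so a within-subject correlation (phi) is needed, and none is given. I use

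- p11 = p1·p2 + phi·√[p1(1−p1)p2(1−p2)], p10 = p1 − p11, p01 = p2 − p11
- d = p10 − p01, s = p10 + p01
- McNemar power ≈ Φ{(d√N − 1.96√s)/√(s − d²)}

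At phi = 0: p10 = 0.255, p01 = 0.105, s = 0.36, d = 0.15. Power = Φ{(1.423 − 1.176)/0.581} = Φ(0.425) = 0.66.

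| phi | Power at N = 90, approximation | Power at N = 90, exact | N for 80%, approximation | N for 80%, exact |
|---|---|---|---|---|
| 0 | 0.66 | 0.60 | 124 | 132 |
| 0.2 | 0.75 | 0.70 | 101 | 110 |
| 0.3 | 0.80 | 0.77 | 89 | 97 |

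The stated 80% appears only with the approximation and an unstated phi of about 0.29. The alternative justification in 9.7.2, effect size 0.5 with N = 90, gives 0.997 by paired t, not 0.80. In any case 30% v 15% is not the contrast that 9.7.1.9 would test, because there the pre rate is 100%.

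**2. The size of the built-in fall.** Let each subject expect λ admissions in 30 days, the same before and after. Counting the index admission, E(pre − post) = (1 + λ) − λ = 1 admission per subject, with no drug effect. As a proportion of subjects hospitalized, the fall is 100% − q, where q is the 30-day readmission rate. At q = 30% that is 70 percentage points.

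**3. Chance of a significant fall with no drug effect.** With pre = 100%, the only discordant pairs are subjects hospitalized before and not after. Their number X is Binomial(90, 1 − q). The exact two-sided McNemar p-value is 2 × 0.5^X: X = 5 gives 0.0625 and X = 6 gives 0.031. So P(significant) = P(X ≥ 6).

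| Assumed q | P(significant fall) |
|---|---|
| 30% | 1.000 |
| 70% | above 0.9999 |
| 80% | 0.9999 |
| 85% | 0.995 |
| 86% | 0.9905 |
| 87% | 0.982 |
| 90% | 0.897 |
| 95% | 0.295 |

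The probability falls to 0.50 only at q of about 94%. An uncorrected McNemar test, or a paired t on 0/1 data, needs only X ≥ 4. That gives 0.992 at 89% and 0.983 at 90%, so the exact test is the cautious illustration.

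**4. After excluding the index admission.** Exact McNemar, N = 90, phi 0 to 0.3, no drug effect:

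| Underlying pre v post rate | P(reject) |
|---|---|
| 15% v 15% | 2.8–3.0% |
| 30% v 30% | 3.0–3.4% |
| 15% v 20% | 10–13% |
| 15% v 30% | 60–77% (false harm) |
| 30% v 15% | 60–77% (false benefit) |

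Exclusion restores the nominal error rate only if the underlying rates are equal.

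**The case against.** Read alone, the phrase about 30 days pre-hospitalization could mean the time before the index admission. The bracketed remark in 9.7.1.9 and the 100% in 9.7.2 rule this out. No other eligibility rule gives every subject an admission within 30 days: criterion 7 accepts an emergency visit and looks back 6 months.

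McNemar is not the planned test, and 90 completers is not the planned analysis set, which is everyone entering Phase B with LOCF. Both points are true. They mean the 86% limit is illustrative, since it moves to about 89% with a paired t. They do not alter the built-in fall.

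The readmission rates are assumptions. The 30% in 9.7.2 is a pre-switch rate with no time window, not a readmission rate, and the documents give no 30-day rate expected without the drug. This stands. But both planning rates, 15% and 30%, are far below the level at which the conclusion would weaken.

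The strongest point is that exclusion does not make the comparison causal. Section 7 says that relapse risk is raised after an acute admission, so equal underlying rates are doubtful. Criterion 7 may also keep the 180-day pre rate high by selection. This stands too, and it limits what the fix can claim.

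**Conclusion.** The concern holds. As written, the primary comparison has a pre-treatment rate of 100% by construction, and a significant fall is close to certain with no drug effect: above 0.99 for any readmission rate up to 86%. This assumes 90 completers, the proportion of subjects hospitalized as the rate (as 9.7.2 uses it), and exact McNemar in place of the planned ANCOVA. The direction depends on none of these choices.

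The defect is in the plan only. The study stopped for slow enrolment with 9 subjects recruited, and no efficacy analysis was performed (Synopsis, 9.7), so no reported result is affected. For the plan, or any reuse of the design, the correction is essential.

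**What to change.** 1. In 9.7.1.9, exclude the index admission from the pre count. End the 30-, 90- and 180-day pre windows the day before it, and extend the claims search to 180 days before that admission. Confirm that the post windows start at discharge, as 9.7.1.1 indicates.
2. State that exclusion restores the nominal error rate only if the underlying pre and post rates are equal, and that the uncontrolled difference cannot by itself be attributed to the drug. Where an earlier discharge exists, add a descriptive pre window starting at that discharge, which is closer to the re-hospitalization objective. Report it with and without the index admission.
3. In 9.7.2, delete the 100% argument. Restate power for 30% v 15% at N = 90, naming the test, the time window and the assumed correlation.
4. As separate clarifications, say that index inpatient days are not counted in the pre-period hospital-days endpoint (the documents do not say they are), and whether the index episode can satisfy criterion 7.

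The cost is SAP wording and a longer claims search. I would restate the power rather than enlarge the trial. Significance is no longer assured, and raised post-discharge risk may work against the drug. Follow-up is 180 days from the start of treatment (9.2), and discharge may come at any time after the first injection (Table 3, note b). A full 180-day window from discharge may therefore pass the last visit and need claims data. The 30-day primary, counted from discharge, is not affected by this.

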## 9.7.1.10 Other Analyses

In general, continuous variables were to be summarized by descriptive statistics (i.e., n, mean, median, SD, standard error, maximum, and minimum). The repeated measures ANCOVA was used based on the Phase B sample. The variables relating to hospitalization data were to be comparing retrospective versus prospective data. The number of hospital stays per subject, cumulative duration of hospitalization, mean duration of hospitalization, and the number and mean duration of all other (i.e., non-inpatient) hospitalization programs were to be compared between the SOC and aripiprazole once monthly by ANCOVA and summarized using descriptive statistics. The Kaplan-Meier estimate of the median discontinuous time and the overall Kaplan-Meier curve for the Phase B efficacy sample were to be provided for the time-to-discontinuation due to all causes. In addition, discontinuation rate due to all reasons, change from baseline in CGI-S and CGI-I scores were to be summarized using descriptive statistics for the Phase B efficacy sample.

## 9.7.2 Determination of Sample Size

The primary endpoints of this study were comparisons of the rate of hospitalization for specified pre-hospitalization (i.e., pre-aripiprazole once monthly) timeframes (i.e., 30-, 90-, and 180-days) to corresponding post-hospitalization timeframes. Based on published results of other studies, it was generally reasonable to assume 30% of subjects would be hospitalized pre-medication switch and 15% would be hospitalized post-switch to aripiprazole once monthly. In this study, 100% of the pre-aripiprazole once monthly subjects would have had at least one hospitalization (i.e., index inpatient hospitalization at least). The estimated sample size of 90 completed subjects would have provided approximately 80% power (alpha = 0.05 two-sided) to detect a clinically relevant difference between pre-switch and post-switch hospitalization rates. The recent Otsuka Mirror study had 121 completers with only a 28% pre-switch hospitalization rate, compared to the present design with a 100% pre-switch hospitalization rate, with highly significant reductions in total psychiatric hospitalization rates in the Mirror study. A medium effect size = 0.5 with a sample size of N = 90 provided approximately 80% power to detect significance at the 5% level (two-tailed test).

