#### 9.2 DISCUSSION OF STUDY DESIGN

The study design, following well-characterized patients for 180 days after starting aripiprazole once monthly treatment, and retrospectively reviewing data regarding prior hospitalizations, psychiatric ED visits, and prior total psychiatric hospitalization days, was planned to allow the proposed hypotheses to be tested adequately.

By utilizing retrospective review of hospitalizations, each subject served as his or her own control. The 30-, 90-, and 180-day analyses allowed for relatively equivalent comparison of the previous 6-month data.

This was an open-label study with one treatment arm, therefore, no active or placebo control or randomization was used. Treatment bias was eliminated via the objective assessments employed.

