# 9.4.3 Method of Assigning Subjects to Treatment Groups

A total of 177 subjects were planned to be enrolled in the study. Subjects were assigned a subject ID number chronologically based on the order of enrollment into the study. The study was a single-arm, nonrandomized study.

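### Section 9.7.2 pairs an effect size of 0.5 with 80% power at N = 90; in this paired single-arm design the power is 99.7% (at least 91% on the other usual scale), and 80% corresponds to about 0.30

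*Combined protocol and SAP*

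**What the plan says.** Section 9.7.2 gives a power of about 80% twice. The first statement is that 90 completed subjects "would have provided approximately 80% power (alpha = 0.05 two-sided) to detect a clinically relevant difference" in hospitalization rates; the size of that difference is not given. The second is "A medium effect size = 0.5 with a sample size of N = 90 provided approximately 80% power", two-tailed at 5%. It gives no SD, scale, test or pre/post correlation for the 0.5.

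Before both statements, the section says that "it was generally reasonable to assume 30% of subjects would be hospitalized pre-medication switch and 15% would be hospitalized post-switch", on the basis of published studies. It then adds that in this study every subject has at least one hospitalization in the pre-period, because of the index admission.

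The design is described elsewhere. In section 9.2, "each subject served as his or her own control". In section 9.4.3, "The study was a single-arm, nonrandomized study". Section 9.7.1.9 says that "all primary and secondary outcome measures described in the specific aims were continuous" and that "The primary and secondary outcomes were to be analyzed using repeated measures analysis of covariance (ANCOVA) models", with a main effect of time (pre versus post) as the primary test. It names one primary comparison among the three time points: "30 days pre-hospitalization (i.e., at least one, based on the index hospitalization) to 30 days post-hospitalization".

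**The concern.** The sentence with the 0.5 holds everything needed to check it: effect, N, alpha, sidedness and power. With one arm and two periods per subject, a main effect of time is a paired comparison. A standardized difference of 0.5 with 90 pairs should give far more than 80% power.

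This is the only explicit effect size in the section that is tied to a power figure. If effect and power do not belong together, a reader cannot tell which effect the 90 completers were chosen to detect. The enrolment target of 177 was set to reach those 90 (section 9.3). Anyone reusing the justification would carry the mismatch forward.

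**Working it through.** **Inputs.** Effect 0.5, N = 90, two-sided alpha 0.05 and stated power of about 80% (section 9.7.2). Paired structure (sections 9.2, 9.4.3, 9.7.1.9). The pre/post correlation is not given, so it is varied as an assumption.

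**1. Effect on the SD of the within-subject difference (dz).** Power comes from the noncentral t with 89 df and noncentrality dz × √N.
- 0.5 × √90 = 4.743, which gives power 0.9968.
- Normal check: Φ(4.743 − 1.960) = Φ(2.783) = 0.997.
- With 88 df, for a CGI-S covariate assumed to explain no variance, power is still 0.9968.
- Completers for 80%: n = 33 gives 0.795 and n = 34 gives 0.808, so 34.

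The stated 80% is not reproduced.

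**2. Effect on the within-period SD.** With equal SDs in the two periods, dz = 0.5 / √(2(1 − ρ)).

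| Assumed ρ | dz | Power at N = 90 | Completers for 80% |
|---|---|---|---|
| 0 | 0.354 | 0.913 | 65 |
| 0.3 | 0.423 | 0.978 | 46 |
| 0.5 | 0.500 | 0.997 | 34 |

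Power of 80% would need ρ = 1 − (0.5 / 0.2985)² / 2, about −0.40.

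**3. Effect that does give 80% at N = 90.** Noncentral t: dz = 0.2985. Normal check: (1.960 + 0.842) / √90 = 0.295. Both are about 0.30.

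**4. Other readings of the sentence.**
- Two independent groups, contrary to the single-arm design: 65.0% with 45 per group, 91.6% with 90 per group.
- Alpha divided by three, within-period SD, ρ = 0: about 82%.
- 0.5 as the ratio 15% / 30%, tested by McNemar: see step 5.

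**5. The 30% versus 15% rates.** For correlation φ, the proportion hospitalized in both periods is p11 = 0.30 × 0.15 + φ√(0.30 × 0.70 × 0.15 × 0.85) = 0.045 + 0.1636φ. Then p10 = 0.30 − p11, p01 = 0.15 − p11, D = p10 + p01 and d = 0.15. The asymptotic power is Φ[(d√90 − 1.96√D) / √(D − d²)].

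At φ = 0.3, D = 0.206 + 0.056 = 0.262, and the power is Φ[(1.423 − 1.003) / 0.489] = Φ(0.859) = 0.805.

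| Assumed φ (maximum 0.64) | Asymptotic McNemar | Exact McNemar |
|---|---|---|
| 0 | 66% | 60% |
| 0.2 | 75% | 70% |
| 0.3 | 80% | 77% |
| 0.5 | 91% | 91% |

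Power of 80% is reached at φ of about 0.29 (asymptotic) or 0.35 (exact). At φ = 0.3 the standardized paired difference is 0.15 / √(0.262 − 0.0225) = 0.31. That is close to the value in step 3, and not 0.5.

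**The case against.** The strongest objection is that the effect size is undefined, so calling the figure wrong depends on a reading the section does not spell out. The rates 30% and 15% stand in the same section, their ratio is 0.5, and McNemar on them reaches 80% at an ordinary correlation. The first power statement may well rest on those rates. A split of alpha over three time points with zero correlation also comes within 2 percentage points of 80%.

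Part of this stands. The scale is missing, and that is itself something to correct. But *medium* is the label for a standardized effect, not for a ratio, and the ratio reading needs a correlation that the plan never states. The alpha split contradicts both the 5% level in the sentence and the single primary comparison in section 9.7.1.9.

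A second objection is that a correlation grid fits the named comparison poorly. If the outcome is the proportion hospitalized, the 30-day pre-value is 1 for everyone, so its SD is zero and the correlation is undefined. That is correct for a binary outcome, but it does not rescue the 80%. With a constant pre-value, the SD of the difference equals the post-period SD. Power is then 99.7% for 0.5 on that SD, and about 91% on the pooled SD, since dz = 0.5 / √2 = 0.354. It does limit what a standardized difference tells the reader. For a binary outcome dz = √((1 − p) / p), so 0.30 would correspond to a post-rate p of about 92%, and 0.5 to 80%.

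A third objection is that nothing depends on the error now: the study ended early and the discrepancy understates power. This is true and limits its importance. It also favors a note over rewriting the record of what was planned.

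**Conclusion.** The concern holds: the power figure is wrong as written for a standardized effect of 0.5. At N = 90 and two-sided 5%, power is 99.7% on the SD of the difference and 91% or more on the within-period SD. The statement is therefore off by about 11 to 20 percentage points. Had 0.5 been the target, 80% power would have needed 34 completers on the difference scale, or up to 65 on the within-period SD, not 90. The 80% figure belongs to about 0.30.

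This rests on reading 0.5 as a standardized pre/post difference, on t-test behavior and, for the within-period scale, on equal SDs and a correlation of 0 or more.

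The 30% versus 15% rates are a separate and lesser point: an undocumented assumption, not an arithmetic error. They are openly taken from other studies and are not the rates of the primary comparison, whose pre-rate is 100% by design. The section does not say whether they underlie the 80%.

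The study was not shown to be undersized. With nine subjects recruited and no formal analysis (Synopsis; section 9.7), only the recorded justification and any reuse of it are affected.

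**What to change.** Because this is a final report, add a correcting note to section 9.7.2. It could read:

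> With 90 completed subjects, a paired comparison has 80% power (two-sided 5%) for a standardized within-subject difference of about 0.30, defined as the mean pre/post difference divided by the SD of that difference. This is the difference detectable with 90 completers, not an effect assumed at planning.

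If 0.5 was the intended effect on that scale, give 99.7% in place of 80%.

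If the 30% and 15% rates are kept as a basis for the 80%, say so. State that they come from other studies and are not the rates of the primary comparison. Name the test, and report power over a correlation range labelled as assumed, as in step 5 of the working.

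The cost is a short note, plus a sentence if the rates are kept. Conduct, data and results do not change.
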